#### 6.3 Efficacy

Efficacy analyses will be based on mITT subjects by as-randomized treatment group only (excluding All BHV-3500 and overall).

Treatment comparisons of binary endpoints will be stratified by prophylactic migraine medication use at randomization except within subgroups. If a single cell has sparse data (< 5 subjects), then the analysis will be performed pooled across strata.

All CIs will be two-sided. In treatment comparisons of binary endpoints, CIs will be based on a normal approximation to the binomial distribution using asymptotic standard error (ASE). In descriptive analyses of binary endpoints, exact Clopper-Pearson CIs will be used. Otherwise, CIs for continuous endpoints will be based on the normal distribution.

A by-subject listing of eDiary migraine characteristics will be provided for randomized subjects that displays parameters listed in Section 7.6.3.2 at migraine attack onset and over time post-dose. The rescue medication start date/time and time to rescue medication use in hours will also be included (see Sections 6.3.4.3 and 7.3); data collected on or after the rescue medication start date/time will be flagged.

Post-dose efficacy data will be slotted into analysis windows automatically by the eDiary (see Section 7.6.3.2). All efficacy endpoints will be assessed using analysis windows, unless specified otherwise.

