9.4 Statistical Methods

9.4.1 Primary Endpoint(s)

Each of the three doses of BHV-3500 is tested for superiority against placebo, at a Bonferroni corrected alpha=0.0167 level, on both pain freedom at 2 hours post-dose and freedom the most bothersome symptom at 2 hours post-dose. Both endpoints are evaluated using Cochran-Mantel Haenszel methodology to estimate the common risk difference, and are stratified by the use of prophylactic migraine medication (yes or no). These tests are conducted using the mITT subjects, with missing data at two hours imputed to be failure (i.e., Non-Completers = Failure; NC=F). Sensitivity analyses are described in the Statistical Analysis Plan (SAP).

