#### 3 POPULATION SAMPLES FOR ANALYSES

The following population samples for analyses ("analysis sets") will be evaluated and used for presentation and analysis of the data:

- Enrolled subjects: Subjects who sign an informed consent form and are assigned a subject identification number, i.e., non-missing informed consent date.
- Randomized subjects: Enrolled subjects who receive a randomization treatment assignment from the interactive web response system (IWRS), i.e., non-missing IWRS randomization date.
- Treated subjects: Enrolled subjects who take study therapy (BHV-3500 or placebo), i.e., non-missing study drug start date/time.
- Modified Intent-to-Treat (mITT) subjects: Treated subjects who are randomized only once, have moderate to severe pain at on-study migraine attack onset, and have non-missing, post-baseline efficacy data (i.e., non-missing pain level, phonophobia status, photophobia status, nausea status, or functional disability level with finding date/time from the eDiary Post-Dose Migraine Report at any time point after the study drug start/time).

See Section 7.3 for derived dates.

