#### **Principal Analyses**

Pain freedom outcomes at 2 hours post-dose will be summarized by treatment group (see Section 6.3.5.2). Outcomes will be summarized analogously for each subgroup level of all efficacy subgroups of interest specified in Section 6.1.3.

The percentages of subjects with pain freedom at 2 hours post-dose will be compared pairwise between each BHV-3500 treatment group and placebo using Cochran-Mantel-Haenszel (CMH) tests stratified by prophylactic migraine medication use at randomization (yes, no). In these analyses, the NC=F and RM=F methods will be applied. The following statistics will be presented:

- Response rate (i.e., "n/N" and percentage), ASE, and 98.3% CI by randomization stratum for each treatment group
- Overall response rate (i.e., "n/N" and percentage), ASE, and 98.3% CI for each treatment group
- Percentage difference between treatment groups (BHV-3500 placebo), ASE, 98.3% CI, and p-value by randomization stratum
- Stratified percentage difference between treatment groups (BHV-3500 placebo), ASE, 98.3% CI, and p-value.

The stratified percentage difference between each BHV-3500 treatment group and placebo will be tested at a Bonferroni-corrected alpha level of 0.0167. A BHV-3500 treatment group will be considered to be superior to placebo for this co-primary endpoint if the p-value for the stratified percentage difference is < 0.0167.

The principal analysis will be repeated unstratified for each subgroup level of all efficacy subgroups of interest specified in Section 6.1.3.

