#### **Sensitivity Analyses**

Sensitivity analyses will include the following:

- Complete cases: The principal analysis will be repeated using NC=M, i.e., subjects who have missing pain level in the 2-hour post-dose analysis window are excluded. First, the RM=F method of handling intervening rescue medication use will be applied. Next, subjects with missing data in the 2-hour analysis window will be excluded. The same statistics as the principal analysis will be presented.
- Multiple imputation: The principal analysis will be repeated using the copy from reference multiple imputation approach with m=20 imputations to impute missing pain data at 2 hours post-dose. The fully conditional specification (FCS) method is used with a generalized logit distribution. Covariates may include prophylactic migraine medication use at randomization (yes or no), sex, pain level at on-study migraine attack onset (moderate or severe), historical number of moderate to severe migraine attacks per month (< median, ≥ median), and MBS at on-study migraine attack onset (nausea, phonophobia, or photophobia). First, the RM=F

method of handling intervening rescue medication use will be applied. Next, missing data in the 2-hour post-dose analysis window will be imputed for subjects who are not missing any of the covariates (subjects missing any of the covariates will be considered failures). The same statistics as the principal analysis will be presented.

• Varying response rate imputation: The principal analysis will be repeated by imputing missing pain data at 2 hours post-dose in each treatment group with varying response rates over the range of 0%, 10%, 20% and 30%. First, the RM=F method of handling intervening rescue medication use will be applied. Next, missing data in the 2-hour post-dose analysis window will be imputed. The following statistics will be presented: stratified percentage difference between treatment groups (BHV-3500 – placebo), ASE, 98.3% CI, and p-value.

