#### **Principal Analyses**

MBS freedom outcomes at 2 hours post-dose will be summarized by treatment group (see Section 6.3.5.2). Outcomes will be summarized analogously for each subgroup level of all efficacy subgroups of interest specified in Section 6.1.3 plus MBS at on-study migraine attack onset (nausea, phonophobia, photophobia).

The percentages of subjects with MBS freedom at 2 hours post-dose will be compared pairwise between each BHV-3500 treatment group and placebo using CMH tests stratified by prophylactic migraine medication use at randomization (yes, no). In these analyses, the NC=F and RM=F methods will be applied. The same statistics will be presented as those for the principal analysis of pain freedom at 2 hours post-dose (see Section 6.3.3.1). The stratified percentage difference between each BHV-3500 treatment group and placebo will be tested at a Bonferroni-corrected alpha level of 0.0167. A BHV-3500 treatment group will be considered to be superior to placebo for this co-primary endpoint if the p-value for the stratified percentage difference is < 0.0167.

The principal analysis will be repeated unstratified for each subgroup level of all efficacy subgroups of interest specified in Section 6.1.3 plus MBS at on-study migraine attack onset (nausea, phonophobia, photophobia).

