## 6.3.4.9 Pain Relapse from 2 to 48 Hours Post-Dose

Pain relapse from 2 to 48 hours post-dose is defined as pain of mild, moderate, or severe at any time point post-dose after 2 hours post-dose for subjects with pain level of none at 2 hours post-dose. Thus, analyses of pain relapse will be based on mITT subjects with pain freedom at 2 hours post-dose (see Section 6.3.3.1).

Subjects who meet all of the following criteria will be classified as non-relapsers:

- Pain level of none at all time points after 2 hours post-dose, i.e., in the 3 to 48-hour post-dose analysis windows
- Missing data at  $\leq 1$  time point after 2 hours post-dose, i.e., in the 3, 4, 6, 8, 24, or 48-hour post-dose analysis window
- No intervening rescue medication taken at or before 48 hours post-dose (see Section 6.3.4.6).

Otherwise, subjects who are not classified as non-relapsers and have any of the following will be classified as relapsers:

- Intercurrent event: Rescue medication taken at or before 48 hours post-dose (RM=F; see Section 6.3.4.6)
- Mild, moderate or severe pain at any time point after 2 hours post-dose, i.e., in the 3, 4, 6, 8, 24, or 48-hour post-dose analysis window
- Missing pain level at > 1 time point after 2 hours post-dose (NC1=F), i.e., in the 3, 4, 6, 8, 24, or 48-hour post-dose analysis window.

Pain relapse from 2 to 48 hours outcomes will be summarized by treatment group as the number and percentage of subjects in the following categories:

- Non-relapser: no pain at all time points after 2 hours post-dose, missing data at ≤ 1 time point after 2 hours post-dose, and no intervening rescue medication taken at or before 48 hours post-dose
- Relapser
  - o Rescue medication taken at or before 48 hours post-dose (RM=F)
  - o Mild, moderate or severe pain at any time point after 2 hours post-dose
    - Severe pain
    - Moderate pain
    - Mild pain
  - $\circ$  Missing pain level at > 1 time point after 2 hours post-dose (NC1=F).

Relapser subcategories are mutually exclusive, because subjects who meet more than 1 relapse criterion will be classified according to the first relapse criterion met; in case of ties, the first relapse subcategory that is met in the hierarchy above will be chosen.

Treatment group comparisons of the percentage of subjects with pain relapse from 2 to 48 hours post-dose will use analogous methods as the principal analysis of the co-primary endpoint of pain freedom with NC1=F and RM=F (see Section 6.3.3.1).

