### 6.3.4.10 Overall Summary of Primary and Secondary Endpoints

An overall summary of treatment comparisons of all primary and secondary endpoints tested hierarchically will present the following statistics:

- Overall response rate (i.e., "n/N" and percentage) and 98.3% CI for each treatment group
- Stratified percentage difference between treatment groups (BHV-3500 placebo), 98.3% CI, and p-value.

Analyses will be based on principal methods described in Sections 6.3.3 and 6.3.4. Endpoints will be displayed in the order presented in Sections 1.2.1 and 1.2.2. P-values that are determined to be significant based on the testing hierarchy will be flagged.

A forest plot of treatment comparisons of all primary and secondary endpoints tested hierarchically will be produced for each treatment group comparison of BHV-3500 versus placebo based on the overall summary. Each plot will display the following statistics:

- Overall response rate (i.e., "n/N" and percentage) for the BHV-3500 treatment group and placebo
- Stratified percentage difference between treatment groups (BHV-3500 placebo) and 98.3% CI.

Percentage differences with p-values that are determined to be significant based on the testing hierarchy will be flagged. Note that each plot will display results for *no* intervening rescue medication use within 24 hours post-dose and *no* pain relapse from 2 to 48 hours post-dose so that positive percentage differences will favor BHV-3500 for these secondary endpoints.

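### The sparse-cell pooling rule in SAP 6.3 leaves unclear which test decides the co-primaries; the effect is small, and always using the stratified test costs almost nothing

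*SAP*

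**What the plan says.** Protocol 9.4.1 evaluates both co-primaries with Cochran-Mantel-Haenszel methods "to estimate the common risk difference, and are stratified by the use of prophylactic migraine medication (yes or no". It has no sparse-data fallback, and the only item it refers to the SAP is the sensitivity analyses.

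SAP 6.3 stratifies every binary comparison by prophylactic use, except within subgroups, and then adds: "If a single cell has sparse data (< 5 subjects), then the analysis will be performed pooled across strata". It does not say whether a cell is a stratum within an arm or also split by outcome. Nor does it say whether pooling is triggered per dose, per endpoint or for all comparisons.

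Under SAP 6.3.3.1 a dose "will be considered to be superior to placebo for this co-primary endpoint if the p-value for the stratified percentage difference is < 0.0167". SAP 6.3.3.2 sets the same condition for MBS freedom. The overall summary in 6.3.4.10 lists only the stratified difference, and there "P-values that are determined to be significant based on the testing hierarchy will be flagged".

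On onset pain, SAP section 3 admits to the mITT set only subjects who "have moderate to severe pain at on-study migraine attack onset". SAP 6.3.3.1 names onset pain level as a possible covariate for multiple imputation, but the principal analysis does not use it.

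**The concern.** If the fallback is triggered, 6.3 calls for a pooled analysis while the superiority rule still names the stratified p-value. Two careful programmers could report different deciding p-values for a registrational endpoint. If cells are outcome counts, the observed responses select the test, and the two co-primaries of one dose, which must both succeed, could be tested by different methods.

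The onset-pain point is separate: a baseline value that is always available and probably prognostic is left out of the principal analysis.

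**Working it through.** **Inputs from the documents.** 380 mITT subjects per arm; pain freedom 12% vs 22%; MBS freedom 32% vs 45%; alpha 0.0167 (0.05/3), taken as two-sided because 98.3% two-sided intervals are planned.

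**Assumptions (not in the documents).** Prophylaxis share 5 to 25%. User/non-user response ratio 0.5 to 1.5 for pain freedom and 0.5 to 1.4 for MBS, with overall rates held at the design values.

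**The plan's power.** The chi-square formula gives 90.1% for pain freedom and 90.3% for MBS freedom. Jointly, 0.901 × 0.903 = 81.4%. The stated 90%, 90% and roughly 80% reproduce.

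**Reading A: cell = stratum within arm.** P(pooled) = 1 − [1 − P(Bin(380, share) ≤ 4)]². This is 2.1% at 3% use, 0.006% at 5%, and effectively zero at 10%.

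**Reading B: cell = stratum by arm by outcome.** Pooling occurs if any of the four counts in the users' 2×2 table is below 5. Simulation with 300,000 trials per scenario gives the share of trials pooled (at ratio 1, with the range over ratios in brackets):

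| Use | Pain freedom | MBS freedom |
|---|---|---|
| 5% | 97% (82–100) | 34% (24–91) |
| 10% | 56% (23–96) | 0.6% (0.1–27) |
| 15% | 19% (4–75) | at most 3% |
| 20% | 5% (0.5–45) | – |
| 25% | 1% (0.1–23) | – |

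At 10% use the two co-primaries of one dose get different methods in 55% of trials at ratio 1 (27% at ratio 1.4, 70% at ratio 0.5).

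**Consequence under reading B, against always stratifying.**
- Power falls by at most 0.2 point (pain) and 0.3 point (MBS).
- The verdict differs in at most 1.0% (pain) and 1.2% (MBS) of trials.
- Type I error is 0.0161–0.0170 with the rule and 0.0161–0.0171 without it (simulation SE 0.0002).

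**Where a fallback has a use.** SAP 6.3.4.9 states that "analyses of pain relapse will be based on mITT subjects with pain freedom at 2 hours post-dose". If that endpoint were always stratified, at least one arm would have no pain-free prophylaxis user in 1 − Π[1 − (1 − share × user pain-free rate)^380] of trials. At ratio 1 this is 11.5% at 5% use, 1.0% at 10% and 0.1% at 15%.

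**Onset pain level.** Assume 25–45% severe, with a severe/moderate response ratio of 0.4–0.6 for pain freedom and 0.6–0.8 for MBS. The variance ratio is the within-severity binomial variance over the total, summed over both arms. Example, pain freedom, 45% severe, ratio 0.4:
- The moderate-pain rate is the overall rate/(0.55 + 0.45 × 0.4) = overall/0.73: 16.4% and 30.1%. The severe rates are 6.6% and 12.1%.
- Within-severity variance: 0.1032 + 0.1635 = 0.2667. Total: 0.12 × 0.88 + 0.22 × 0.78 = 0.2772.
- Reduction: 1 − 0.2667/0.2772 = 3.8%.

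Over the ranges, variance falls 0.8–3.8% (pain) and 0.5–3.9% (MBS). Wald power rises from 90.5% to 90.7–91.6% and from 90.7% to 90.9–91.9%, a gain of about 0.2 to 1.2 points. The Wald baselines lie slightly above the chi-square figures of 90.1% and 90.3%.

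**Price of four strata.** P(at least one arm has fewer than 5 subjects who are users with severe pain) = 1 − [1 − P(Bin(380, share × severe share) ≤ 4)]². At 5% use this is 73% (25% severe) or 13.5% (45% severe); at 10% use, 7.6% or 0.03%. An empty arm cell occurs in 1.7% of trials at 5% use and 25% severe, and in 0.04% or less in the other three cases.

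**The case against.** SAP 6.3 opens the efficacy section and governs what follows. It says that the analysis itself is pooled, so the pooled result can be read as replacing the stratified one in 6.3.3. A SAP may also add a pre-specified rule where the protocol is silent. Both points stand. A reader might infer that the SAP contradicts the protocol, or that a pooled p-value can never decide. The documents support neither: there is an addition to reconcile and a cross-reference that is missing.

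A reader might also infer from the high pooling percentages that the test choice inflates type I error or undermines the 90% power. The working shows neither. Those percentages need reading B and a low prophylaxis share. Reading A fits a threshold expressed in subjects at least as well, and under it the rule practically never reaches the co-primaries.

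For pain relapse, defining a cell as evaluable subjects still lets 2-hour pain-free counts trigger pooling: in 97%, 56% and 19% of trials at 5%, 10% and 15% use (ratio 1). That is correct. The trigger is then the denominator rather than the relapse outcome, and relapse is the last of 15 secondaries, so it is tolerable if written down.

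Finally, analysing by the randomisation factor alone is standard, and onset-pain adjustment is optional. This also stands: its absence is not a defect.

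**Conclusion.** The point holds as a small ambiguity. An undefined word moves the chance of pooling pain freedom at 10% use from essentially zero to 56% (23–96% over the assumed ratios), yet the result hardly depends on it. What survives is that always analysing the co-primaries by the randomisation strata has no material cost and stops responder counts from choosing the test. The sample-size figures are unaffected.

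The onset-pain adjustment is a modest separate gain that rests on assumed severe shares and response ratios. It is worth having only without the below-5 rule, which four strata would often trigger if prophylaxis use is low.

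**What to change.** Before unblinding:

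1. State in SAP 6.3 that the pooling fallback does not apply to the two co-primaries, so that the Mantel-Haenszel risk difference stratified by prophylactic use always decides. If the fallback is kept for secondaries with small denominators, define a cell as subjects evaluable for that endpoint per stratum and arm, and say that the pooled p-value then decides that step of the hierarchy. Cost: SAP wording only.

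2. Optionally, also adjust both co-primary analyses for onset pain level (moderate, severe), using Mantel-Haenszel weights or a covariate-adjusted risk difference without the below-5 rule. No new data are needed, but protocol 9.4.1 must be aligned. Under protocol section 11 that means an amendment submitted to the IRB/IEC, with approval awaited. The SAP must also say how the recalled pain level is used for subjects who dosed before opening the eDiary (SAP 7.6.3.2).

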## 6.3.5.2 Efficacy at Each Post-Dose Time Point

## **Efficacy Outcomes Over Time: Principal Analyses**

Efficacy outcomes will be summarized for mITT subjects by treatment group as the number and percentage of subjects in categories (responder; failure; failure subcategories) at each time point from 15 minutes through 48 hours post-dose. Subjects who are not classified as responders at a time point will be classified as failures. Failure subcategories are mutually exclusive, because subjects who meet more than 1 failure criterion will be classified according to the first failure criterion met; in case of ties, the first failure subcategory that is met in the specified hierarchy for an endpoint will be chosen. Percentages for response rates will also be shown with exact Clopper-Pearson 98.3% CIs.

Outcomes will be presented separately for each of the following efficacy endpoints: pain freedom, MBS freedom, pain relief, nausea freedom, phonophobia freedom, photophobia freedom, and return to normal function. These analyses will use the NC=F and RM=F methods to align with principal analyses of co-primary and secondary endpoints (see Sections 6.3.3.1 and 6.3.3.2). Outcomes category nomenclature is as follows:

- "at time point" means in the analysis window corresponding to that post-dose time point
- "No intervening rescue medication taken at or before time point" means rescue medication start date/time missing or > {eDiary finding date/time in the analysis window corresponding to that post-dose time point}
- "Rescue medication taken at or before time point" means (rescue medication start date/time study drug start date/time) ≤ upper bound of the analysis window corresponding to that post-dose time point (see Section 7.5).

Outcomes for mITT subjects will be presented over time as described below. Subjects who are not included in the mITT population sample will have the following outcomes in by-subject listings:

- Randomized subjects not in the mITT population sample: "Not mITT"
- mITT subjects with absent or missing symptom status at on-study migraine attack onset for nausea freedom, photophobia freedom, and photophobia freedom: "Not evaluable: symptom absent at onset" or "Not evaluable: symptom missing at onset"
- mITT subjects with normal or missing functional disability level at on-study migraine attack onset for return to normal function: "Not evaluable: normal function at onset" or "Not evaluable: missing disability level at onset".

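### Per-arm response rates in the treatment-comparison tables get normal-approximation 98.3% CIs that under-cover in small groups with low rates, and the same arm and subgroup rates get exact CIs in the outcomes tables

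*SAP*

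**What the plan says.** SAP 6.3 names two methods. For comparisons, "In treatment comparisons of binary endpoints, CIs will be based on a normal approximation to the binomial distribution using asymptotic standard error (ASE". For the rest, "In descriptive analyses of binary endpoints, exact Clopper-Pearson CIs will be used". It also states that "All CIs will be two-sided".

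The pain-freedom comparison in SAP 6.3.3.1 lists more than between-arm differences. It asks for each arm's response rate with "ASE, and 98.3% CI by randomization stratum for each treatment group", and for the overall rate with "ASE, and 98.3% CI for each treatment group". The table is then carried into subgroups: "The principal analysis will be repeated unstratified for each subgroup level of all efficacy subgroups of interest specified in Section 6.1.3". SAP 6.3.3.2 applies the same statistics to MBS freedom, most secondary endpoints use analogous methods, and 6.3.4.10 collects the overall rates and CIs in one summary.

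SAP 6.3.5.2 tabulates the same 2-hour responder rates, in the same mITT arms and under the same NC=F and RM=F rules. There, "Percentages for response rates will also be shown with exact Clopper-Pearson 98.3% CIs". SAP 6.3.3.1 extends those outcomes tables too: "Outcomes will be summarized analogously for each subgroup level of all efficacy subgroups of interest specified in Section 6.1.3".

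The complete-case part of 6.3.5.2 says that its 2-hour co-primary results will match the complete-case sensitivity analyses of 6.3.3.1 and 6.3.3.2. It shows them with Clopper-Pearson intervals, whereas 6.3.3.1 gives that sensitivity analysis the statistics of the principal (ASE-based) analysis.

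Two rules limit small groups. In 6.3, a cell with fewer than 5 subjects leads to pooling across strata. In 6.1.3, subgroup levels may be redefined or combined, with no numerical threshold.

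**The concern.** The simple normal-approximation (Wald) interval for one proportion is known to perform badly when few responders are expected. Placebo pain freedom is planned at 12%, and the stratum and subgroup tables cut each arm of about 380 into smaller groups. Three things can go wrong there: the interval covers the true rate less often than 98.3%, its lower limit can fall below zero, and it collapses to a point when no one responds.

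In addition, one arm-level or subgroup-level 2-hour rate will appear in the study report with two different intervals, both labelled 98.3%. What is at stake is the stated precision of descriptive rates and the consistency of the tables, not the test of superiority.

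**Working it through.** **Inputs**
- From SAP 5: about 380 mITT subjects per arm; pain freedom 22% vs 12%; MBS freedom 45% vs 32%; alpha 0.0167.
- From SAP 6.3.3.1: 98.3% level, so z = 2.387 for a two-sided error of 1.7%.
- Assumed: group sizes below 380, because the documents give no stratum or subgroup sizes. If 10% to 20% of subjects used prophylaxis (also assumed), that stratum would hold 38 to 76 per arm.

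**Plan figures reproduced first.** The SAP states no coverage for these intervals. Its related figures do reproduce. With 380 per arm and alpha 0.0167, two-sided power is 90.1% for 22% vs 12% and 90.3% for 45% vs 32%, and 0.901 × 0.903 = 0.814 jointly under independence. The level also agrees: 1 − 0.05/3 = 0.983.

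**Formula.** With x responders of n and p̂ = x/n, the Wald interval is p̂ ± 2.387·√(p̂(1−p̂)/n). Its true coverage at rate p is the sum of the binomial probabilities of every x whose interval contains p.

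**Example, n = 10, p = 0.12.** The interval at x = 0 is the single point 0 and misses. The intervals at x = 1 to 4 contain 12% (x = 4 gives 3.0% to 77.0%). At x = 5 it is 12.3% to 87.7% and misses. Since P(X=0) = 0.88^10 = 27.85% and P(X≥5) = 0.37%, coverage is 100 − 27.85 − 0.37 = 71.8%.

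**Why n = 30 is worse than n = 20.** One responder of 20 gives an upper limit of 16.6%, which contains 12%. One of 30 gives 11.2%, which does not. At n = 30 the misses are P(X≤1) = 11.00% and P(X≥10) = 0.19%, so coverage is 88.8%.

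**Coverage (%) of the nominal 98.3% Wald interval**

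| n | 12% | 22% | 32% | 45% |
|---|---|---|---|---|
| 10 | 71.8 | 90.6 | 96.3 | 94.9 |
| 20 | 92.1 | 94.8 | 96.7 | 96.0 |
| 30 | 88.8 | 97.2 | 97.8 | 97.4 |
| 60 | 93.8 | 96.5 | 98.0 | 98.0 |
| 100 | 96.0 | 98.0 | 97.4 | 98.0 |
| 380 | 97.9 | 98.3 | 98.1 | 98.2 |

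Clopper-Pearson coverage was at least 98.3% at every size and rate tried.

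**Boundary behaviour at 12%.** The probability of a zero-width interval is 27.9% at n = 10 and 0.88^20 = 7.8% at n = 20. With no responders, the exact interval would run from 0 to 37.9% and from 0 to 21.2%. At n = 20 the Wald lower limit is negative in 84% of samples.

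**The two methods on the same count**

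| Count | Wald | Clopper-Pearson |
|---|---|---|
| 2/20 | −6.0% to 26.0% | 0.7% to 36.5% |
| 3/10 | −4.6% to 64.6% | 4.5% to 71.1% |
| 46/380 | 8.1% to 16.1% | 8.4% to 16.7% |

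At 380 per arm, across the four planning rates, no limit moves by more than about 0.6 points.

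**Differences between arms.** The same enumeration for the Wald interval of the unstratified difference, at 22% vs 12%, gives 97.3% coverage at 20 per arm, 97.9% at 40 and 98.25% at 380. The interval for the difference performs much better than the per-arm one.

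**The case against.** The strongest reply is that nothing rests on these intervals. Superiority is judged on the p-value for the stratified percentage difference, so type I error, power and the testing sequence are untouched. That stands in full.

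A reader might infer that the SAP contradicts itself on the main endpoint. The text does not support this. Section 6.3 openly assigns one method to comparisons and another to descriptive analyses. Two intervals for one rate are the result of a stated convention, and at 380 per arm they nearly coincide. The only sentence that cannot hold as written is the one in 6.3.5.2 saying the 2-hour complete-case results will be the same, and it fails only for the CIs.

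A reader might also extend the duplication to the prophylaxis strata. No part of the SAP gives exact intervals by stratum; the duplication concerns arm and subgroup rates only.

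Nor are the Wald intervals always too narrow. At 3/10 the Wald width is 69.2 points before truncation at zero, against 66.6 for the exact interval. The fault is under-coverage, poor centring and behaviour near zero.

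Finally, the worst figures belong to the 12% rate, the small group sizes are assumed, and 6.1.3 allows levels to be combined. All of this limits the size of the point. It does not remove it: the pooling rule cannot help subgroup analyses that are already unstratified, and the combining rule has no threshold. SAP 6.1.3 also lists Asian as a race level of its own, and pain relapse (6.3.4.9) is analysed only in subjects who are pain-free at 2 hours, about 0.12 × 380 = 46 on placebo at the planning rate, before any split by stratum.

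**Conclusion.** The point holds as a minor, presentational one. Each arm's own rate in the comparison tables gets a normal-approximation 98.3% interval. For pain freedom at 12% its coverage is 71.8% to 93.8% over n = 10 to 60. At 22% it is 90.6% at n = 10, 94.8% at n = 20 and 97.2% at n = 30. For rates of 32% to 45% it is about 96% to 98% from n = 20. The interval can have a negative lower limit, and it has zero width with no responders.

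The coverage figures are exact for the stated rates and sizes. Whether groups this small occur is an assumption, since the documents give neither prophylaxis use nor subgroup sizes. The overall arm-level intervals are adequate in practice at about 380 subjects.

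The 2-hour arm and subgroup rates will carry two 98.3% intervals in the report, and the complete-case statement in 6.3.5.2 needs correcting. It would be wrong to conclude that any test, the power or a superiority decision is affected.

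**What to change.** - In SAP 6.3 and 6.3.3.1, and through them 6.3.3.2 and the secondary endpoints, specify Clopper-Pearson 98.3% intervals for every per-arm response rate based on an integer count: overall, by stratum, by subgroup level, in the complete-case analyses and in the 6.3.4.10 summary.
- Keep ASE-based intervals for the percentage differences.
- Make an explicit exception for the multiple-imputation tables. Section 6.3.3.1 gives them the same statistics as the principal analysis, but rates pooled over 20 imputations have no single integer count, so an ASE-based interval should stay there.
- Align the complete-case statement in 6.3.5.2. Once the per-arm intervals are exact in both places, it can stand for the response rates and their CIs.

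The cost is SAP wording and a small programming change, using a method the SAP already specifies. Clopper-Pearson is conservative (99.3% coverage at n = 20 and n = 30 for a 12% rate), so most per-arm intervals become somewhat wider. No hypothesis test changes.
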